Power and Sample Size Estimates. A within-subject design is used to evaluate the physician intervention and a randomized control trial is used to evaluate the patient intervention. However, the outcomes of both interventions will be modeled at the patient level in a single model. We used the person-level multi-site/block trial design within Optimal Design to conduct power analyses because the unit of analysis is the patient-physician visit and data from these visits will likely be more similar within physicians than between physicians. The first power analysis is based 216 patients not lost to attrition, who should be eligible for clinical trials and thus randomized into the patient-level intervention. (See Participants and Recruitment—p. 7) We define the *primary outcome* of our study as patients' decisions to enroll in clinical trials, where a "success" is defined as a patient deciding to enroll. Our primary objective (Aim 1) is to examine the extent to which patient- and physician-level interventions affect physician and patient trial-related decisions, and thus we seek a sample size that gives us sufficient power to detect both the main effect of intervention and important interaction effects. We chose GEE power analysis for nested binomial outcomes with within-cluster treatments⁶⁶ as the best available model to estimate power for our primary objective; such estimates are lacking for HLM models. With 24 physicians and 9 patients per physician (i.e., 216 patients), a Type I error rate (α) of .05, and ICC of .05, and probability of success under the null hypotheses (p_{H_0}) of .25, we are well powered to detect p_H of .35 ($b = 0.48$, odds-ratio = 1.61) with power > .99. Our secondary objective, (i.e., Aim 2) is to examine whether patient race influences the effectiveness of either patient- or physician-level interventions on our primary outcome, and we remain well

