powered to detect 2-way and 3-way interactions. We will also examine effects of the interventions, and between-race differences in effects of the interventions on other binary or continuous outcomes (e.g., trial offers, patients' perceptions of patient-centeredness, perceived involvement in care, trust in physician, etc.). The power analysis described above holds for the binary outcomes. For the continuous outcomes, we used block person-randomized trial module in Optimal Design⁶⁷ to estimate power. Considering each of the 24 physicians as "blocks" and assuming about 9 patients per physician, a Type I error rate (α) of .05, between-physicians variability in effect size (σ_{β}^2) of .05, 5% of variance in outcomes due to physicians and a medium effect size (d) of .50, power to find effects exceeds .90. Our final objective, (Aim 3) is to explore the extent to which patient-physician communication mediates the effects of the interventions on the outcomes. We will use Multi-level Structural Equation Modeling (MSEM) that control for patient-physician nesting to fit path analyses. The specific structure (i.e. direct and indirect paths of the models) will be guided by results from analyses conducted for our first and second aims. We therefore consider the MSEM exploratory in that we are the first researchers to examine these effects in this context. Thus, at this point we lack the specification of the model parameters needed to provide accurate estimates of power for this exploratory aim.

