Control variables: At the patient level of the model, we will control for factors such as decisional control preferences, relevant attitudes, health literacy, number of boosters received, disease severity, co-morbidities, whether there is an available clinical trial for the patient, and if so, characteristics of the trial (e.g., difficulty, complexity). At the physician level, we will control for relevant racial and professional attitudes, and decisional control preferences. Because the physician-focused phase involves a quasi-experimental design, we will also control factors that might threaten the internal validity of the intervention, such as time since study has begun, and number of previous interactions between patients and physicians.

Hypothesis 1a. Outcomes will be significantly improved in the patient intervention group, relative to the usual care group. To test hypothesis 1a, we will fit separate MLMs to examine continuous and binary outcomes assessed during or after each visit in which a trial was discussed. The focal independent variable will be the dummy-coded variable indicating whether the patient was in the usual care or intervention group. Support for hypothesis 1a will be indicated by a significant coefficient for this independent variable (i.e. intervention/usual care).

Hypothesis 1b. Outcomes will be significantly improved for patients after the physician intervention, as compared to outcomes before the physician intervention. The focal independent variable is the dummy-coded variable indicating whether or not the patient's physician has received the physician intervention at the time of the clinic visit. Note that this variable is a within-subject variable among the physicians; however, because we theorize that the patient-physician communication quality is central to offers and acceptance of clinical trials, this variable is introduced in the model at level-1 (patients). Support for hypothesis 1b will be indicated by a significant physician-intervention coefficient (i.e., pre/post physician intervention).

Hypothesis 1c. The combined effects of the two interventions will be multiplicative, rather than simply additive. The focal independent variable is the dummy coded variable for the product interaction term in the model. We expect the physician intervention to be more effective among patients who received the patient intervention; we expect a statistically significant positive coefficient for the interaction term.

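### The stated power above .99 for the primary outcome (25% vs 35%, 216 patients) is wrong: the plan's own inputs give about 38% two-sided

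*Combined protocol and SAP*

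**What the plan says.** Under Statistical Analyses, Power and Sample Size Estimates, the primary outcome is the patient's decision to enrol in a clinical trial. The layout and error rate are given as "With 24 physicians and 9 patients per physician (i.e., 216 patients), a Type I error rate (α) of .05, and ICC of .05". The success probability under the null is .25, and the method is a GEE power calculation for clustered binary data with treatment varying within the cluster. The conclusion is that "we are well powered to detect p_H of .35 ($b = 0.48$, odds-ratio = 1.61) with power > .99".

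The section then builds on this result. It says that two-way and three-way interactions remain adequately powered, and, for outcomes such as trial offers, that "The power analysis described above holds for the binary outcomes". For continuous outcomes it uses the same 24 x 9 layout and reports "a medium effect size (d) of .50, power to find effects exceeds .90".

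The analysis sections that follow define the tests. For the randomised comparison, "Support for hypothesis 1a will be indicated by a significant coefficient for this independent variable". The physician intervention is tested by a pre/post indicator in the same model. The Control variables paragraph adds adjustment for threats to validity "such as time since study has begun, and number of previous interactions between patients and physicians".

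**The concern.** A 10-point difference between two groups of 108 is a small effect for a sample of this size, so power above .99 is implausible on sight. Randomising within physician removes between-physician variance, but with an ICC of .05 the gain is only 5% of the variance.

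The section's two results also do not fit together. Power is put just above .90 for a standardised effect of .50, yet above .99 for 25% vs 35%. On Cohen's scale that is h = 2 arcsin(√.35) − 2 arcsin(√.25) = .22, less than half as large.

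This is the only power figure given for the primary outcome, so the sample size rests on it. If it is wrong, a non-significant hypothesis 1a or 1b would be reported as a near-certain negative when a real 10-point gain could easily have been missed.

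**Working it through.** **Inputs.** From the power section: 24 x 9 = 216 patients, already net of attrition; alpha .05; ICC .05; .25 vs .35. Not stated, so assumed: a two-sided test and 1:1 allocation within physician (108 per group, about the most favourable split).

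**Effect size.** The odds ratio is (.35/.65)/(.25/.75) = 1.615 and its log is 0.480. Both match the plan, so .35 is not a misprint.

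**Power for the two-group contrast.** Treatment within cluster multiplies the variance by (1 − ICC) = .95.

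- Variance = (.25 x .75 + .35 x .65)/108 x .95 = .4150/108 x .95 = .00365; SE = .0604
- z = .10/.0604 = 1.66
- Two-sided power = Φ(1.66 − 1.96) = .38
- One-sided power = Φ(1.66 − 1.645) = .50

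Other methods agree on the two-sided figure: pooled two-proportion formula .376, logit Wald .374, GEE sandwich variance .373, and a 20,000-run simulation with a physician-stratified test .370. Ignoring the ICC gives .36.

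**Can any reading reach .99?**

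| Reading | Two-sided power |
|---|---|
| 32 physicians x 9 | .47–.48 |
| 216 per group | .64–.65 |
| All 440 recruited patients | .65–.66 |
| One-sample test of 216 against 25% | .90–.92 (one-sided at most .95) |
| 216 clusters of 9 (1,944 patients) | .998 |
| ICC of .9 | .996 |

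Only the last two pass .99, and both contradict the stated inputs.

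**Sample size for 25% vs 35%.** N = 2 (1.96 + z_power)² x .4150 x .95/.10². This gives 619 for 80% power, 829 for 90% and 1,449 for 99%. The pooled formula gives 625, 836 and 1,457.

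**Detectable effect with 216.** Solving the same equation for the second rate gives about .42 at 80% power (odds ratio about 2.2) and about .52 at 99%.

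**The continuous-outcome figure.** The noncentrality is λ = d²/[(σ_β² + 4/9)/24] = .25/[(.05 + .444)/24] = 12.1, with F on 1 and 23 df. Power is .915, or .927 if the residual variance is .95. The stated value above .90 therefore reproduces; only the binary figure fails.

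**Hypothesis 1b with calendar time in the model.** The introductory summary gives 20 months before, 2 months of intervention and 20 months after. Assume visits spread evenly over months 0–20 and 22–42, and a linear time term.

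- Phase means are months 10 and 32, so between-phase variance = 11² = 121; within-phase variance = 20²/12 = 33.3
- R² = 121/154.3 = .784; variance inflation = 1/(1 − .784) = 4.63
- Effective N = 216/4.63 ≈ 47; z = 1.655/√4.63 = 0.77; power ≈ .12

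If visits fell only in the first 10 months of each phase, the within-phase variance would be 10²/12 = 8.3, the inflation 15.5 and power about .07.

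**Coding and interactions.** With 0/1 dummies and a product term, the patient-intervention coefficient is the effect in one phase only. With 54 per group, z = 1.66/√2 = 1.17 and power is about .21. For an interaction as large as the main effect (log odds ratio 0.48, an assumed size), the variance is 4 times larger for a two-way term and 16 times for a three-way term. Power is then about 13% and 6%.

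**The case against.** - **Sidedness is not stated and the hypotheses are directional.** This stands as a qualification. At one-sided .05 power is about .50, so missing the effect becomes an even chance, not the likelier result. It does not bring .99 within reach.
- **The 38% is for a simple two-group contrast, not the planned model.** This is correct. Hypothesis 1a is tested in a model with a product term, and the participation decision is also listed for multinomial regression with an undecided category. The 38% must be labelled accordingly. Literal dummy coding lowers it to about 21%.
- **The hypothesis 1b figure is not derived from the plan's inputs alone.** This also stands. The plan gives no form for the time adjustment and no distribution of visits, so .12 is illustrative. Recruitment as early as possible in each phase points to front-loaded visits, which make it worse. The calculation is introduced for patients randomised to the patient intervention, so it is arguable whether the stated power was meant for hypothesis 1b. The same paragraph, however, names both interventions as its objective.
- **The binary and continuous calculations use different methods.** They do, so the mismatch is supporting evidence and not a literal contradiction. The slope variance of .05 in the continuous calculation is too small beside 4/9 to explain it.

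How the stated figure arose cannot be told from the document.

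**Conclusion.** The stated power is wrong. On the plan's inputs, with a two-sided test and 1:1 allocation, 216 patients give about 38% power for 25% vs 35%, so the planned effect would more likely than not be missed. A one-sided test raises this to about 50%. No reading that keeps the stated inputs comes near .99, which would need about 1,450 patients.

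The claims for other binary outcomes and for interactions fall with it. For hypothesis 1b the exact value depends on assumptions about visit timing and the time term. What is certain is that the power section makes no allowance for the overlap between the pre/post indicator and calendar time. This must be corrected, because it is the figure that justifies the sample size.

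**What to change.** 1. Replace the power statement: 216 patients give about 38% power (two-sided .05, 1:1 within physician, ICC .05, simple two-group contrast) for .25 vs .35, and 80% power for about .25 vs .42 (odds ratio about 2.2). State the sidedness and allocation ratio.
2. Say how the intervention indicators are coded and which coefficient tests hypothesis 1a, and give the power for that coefficient.
3. Give hypothesis 1b its own power figure with the time covariate in the model, as a range over stated visit patterns.
4. Delete or recalculate the statements that the result carries over to the other binary outcomes and to two-way and three-way interactions.
5. Report hypotheses 1a and 1b with confidence intervals. For the simple contrast the 95% half-width is about 1.96 x .0604 = 12 points, so a null result will often not exclude a 10-point effect.

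The cost is protocol wording and a less favourable power statement. Correcting the statement needs no extra patients; raising power to 80% would need about 620 analysed patients, which is a separate decision for the sponsor.

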We will use Multi-Level Models (MLMs) that include separate variables identifying both interventions, as well as a variable indicating the interaction between the two phases. This model allows us to examine the main effect of each intervention, and multiplicative effects of having been exposed to both interventions. For purposes of clarity, we discuss hypotheses for each intervention separately, but as already noted, they will be tested in the same MLMs. We will model most outcomes (specifically, patients' perceptions of patient-centeredness, perceived involvement in care, trust in physician, and team perceptions; patient active participation, and physician patient centeredness, patient understanding of informed consent) as continuous variables. We will use binomial logistic models for binary outcomes (e.g., trial offer) and multinomial logistic regression for categorical outcomes (e.g., patients' self-reported participation decision - "yes", "no", "undecided"). We will also explore whether a single model best captures the meditational processes for both Black and White patients or separate models are needed.

Models for Aim 1: As we have described the objectives and outcomes above, here we generally describe the models that will be used to test support for our hypotheses. All outcomes, and coefficients for each of the intervention effects and interactions between them, will be modeled at the patient level of the model (level-1); that is, they will be nested within physicians (level-2). We will use one MLM for each outcome to test the three Aim 1 hypotheses. We use this particular approach to examine the interventions' effects because it is believed that the two interventions will not only work independently, but also interactively. Thus, we use a model that simultaneously controls for the main and interactive effects of both interventions as we examine their unique contributions.

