Models for Aim 2: Hypothesis 2 (African American – White Differences) - Effects of the intervention will be significantly greater among African American than White men. We will test the hypothesis by introducing 2-way interactions between race and patient- and physician-focused interventions, and a 3-way race by patient-focused by physician-focused intervention variable, to the models. A significant coefficient for the 2-way interaction between race and the patient-focused intervention, will indicate whether the magnitude of the intervention is influenced by patients' race. The coefficient for the 3-way interaction will be used to assess whether the magnitude of the interactive effect of the patient- and physician-focused interventions depends on patients' race. We will probe the specific nature of these interactions with methods outlined by Preacher, et al.¹⁶⁹ We will also explore the moderating effects of other patient level variables (e.g., socio-demographics, race-related attitudes, etc.) in separate analyses.

Models for Aim 3: Hypothesis 3 (Mediating effects of patient-physician communication): The quality of patient-physician communication will mediate the effect of the interventions on trial offers, and, in turn, on patient understanding of trials offered and decisions to participate. We will use Multilevel Structural Equation Modeling (MSEM) to assess mediational/indirect effects. We will examine the specific relationships (paths) specified within the models as well as how well the overall model fits the data; we will use standard indices of the quality of fit (e.g. RMSEA, CFI). We will utilize observational measures of communication quality and relevant patient's perceptions of the interaction (see measures above) as measures of the mediating variables of the interest in the model. Separate models will be used for each outcome. Separate models will be conducted for separate outcomes.

References

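### The claim of good power for race-by-intervention interactions (Aim 2, primary outcome) has no calculation behind it and fails for an interaction of the planned main-effect size

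*Combined protocol and SAP*

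**What the plan says.** All places are in the combined protocol and SAP, under Statistical Analyses.

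- **Power and Sample Size Estimates, main effect.** With 24 physicians, 9 patients each (216 in all), α .05, ICC .05 and a null success rate of .25, the plan says "we are well powered to detect p_H of .35" (b = 0.48, odds ratio 1.61) with power above .99.
- **Same section, Aim 2.** The secondary objective is given as follows: "examine whether patient race influences the effectiveness of either patient- or physician-level interventions on our primary outcome, and we remain well". The sentence then runs on to the claim itself, which describes the study as suitably "powered to detect 2-way and 3-way interactions". No interaction size, cell rate, cell size or power value follows. The next calculation (d = .50, power above .90) is for continuous outcomes and is not described as an interaction.
- **Model description.** "We will use binomial logistic models for binary outcomes". The same sentence assigns multinomial regression to the self-reported participation decision (yes, no, undecided).
- **Hypothesis 1a.** "The focal independent variable will be the dummy-coded variable indicating whether the patient was in the usual care or intervention group". Hypothesis 1b dummy-codes the physician intervention in the same way.
- **Models for Aim 2.** The test of Hypothesis 2 consists of "introducing 2-way interactions between race and patient- and physician-focused interventions, and a 3-way race by patient-focused by physician-focused intervention variable, to the models". Whether race changes the size of the patient-intervention effect is then judged from one of these terms, the criterion being "A significant coefficient for the 2-way interaction between race and the patient-focused intervention". For the highest-order term the rule is: "The coefficient for the 3-way interaction will be used to assess whether the magnitude of the interactive effect". The interactive effect meant there is the one between the two interventions, compared by race.

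**The concern.** A calculation for a main effect does not carry over to an interaction. An interaction is a difference between differences, estimated from smaller cells, and a 3-way term is a difference between two of those. With the same patients and the same effect size, its standard error is several times larger. The plan moves from one main-effect figure to a claim about 2-way and 3-way terms without naming the interaction it has in mind.

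Hypothesis 2 is a formal, directional hypothesis decided by the significance of these coefficients. The power section also says that the sample size was sought with important interaction effects in view. A reader told that power is good would give a non-significant race interaction more weight than it can bear. Such a reader would also not know that, under the assumptions below, an estimated ratio of odds ratios must exceed about 3.1 (averaged 2-way), 5.0 (2-way at reference level) or 9.7 (3-way) to reach two-sided significance.

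**Working it through.** **Inputs from the documents.** 216 patients; α .05; ICC .05; rates .25 and .35; both interventions dummy-coded. Recruitment is planned as 220 African American and 220 White patients, half before and half after the physician intervention.

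**Assumptions not in the documents.** Equal cells among the 216, 1:1 patient allocation, a two-sided test (one-sided also shown), a mean rate near .30 so that p(1−p) = .21, and no covariates. The interaction is set equal to the planned main effect on the log-odds scale.

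**Step 1. The plan's own figure.** b = ln[(.35/.65)/(.25/.75)] = .480, odds ratio 1.615; these agree with the plan. For 108 against 108, the variance is .95 × [1/(108 × .1875) + 1/(108 × .2275)] = .0856, so SE = .293, z = .480/.293 = 1.64 and two-sided power is about .37. The stated figure above .99 does not reproduce. That is a separate point; Step 5 shows that the present one does not depend on it.

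**Step 2. Which cells each coefficient uses.**
- 2-way, no 3-way term in the model: averaged over the other intervention; four cells of 216/4 = 54.
- 2-way, dummy-coded, 3-way term in the model: the interaction at the reference level of the other intervention; four cells of 216/8 = 27.
- 3-way: eight cells of 27.

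**Step 3. Power at b = .480.** SE = √[k × (1 − ICC)/(p(1−p) × n)] for k cells of n. Two-sided power = Φ(b/SE − 1.96) + Φ(−b/SE − 1.96).

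| Term | SE | b/SE | Two-sided | One-sided |
|---|---|---|---|---|
| 2-way averaged | √[4 × .95/(.21 × 54)] = .579 | .83 | .13 | .21 |
| 2-way at reference level | √[4 × .95/(.21 × 27)] = .819 | .59 | .09 | .14 |
| 3-way | √[8 × .95/(.21 × 27)] = 1.158 | .41 | .07 | .11 |

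For mean rates from .25 to .35 the two-sided values are .12 to .14, .09 and .07. Logistic simulation with a physician random intercept gave .12, .08 and .07. Using all 440 recruits instead of 216 gives about .21 (2-way averaged) and .09 (3-way). The significance thresholds given above are exp(1.96 × SE) = 3.1, 5.0 and 9.7.

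**Step 4. Size needed for 80% power.** exp[(1.96 + .84) × SE] gives ratios of odds ratios of about 5, 10 and 26. The normal approximation is optimistic for the 3-way term. With a base rate of .25 and one cell carrying the effect, a likelihood-ratio test reaches about .74 at a ratio of 32 and .84 at 60, so the ratio needed is roughly 30 to 60.

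**Step 5. Granting the main-effect claim.** Suppose main-effect power were .99, so that z = 1.96 + 2.326 = 4.286. The answer depends on which main effect is meant.
- *Marginal 108-against-108 contrast.* The interaction variances are 4, 8 and 16 times larger (averaged, reference level, 3-way). Dividing z by 2, √8 and 4 gives power of .57, .33 and .19.
- *Dummy-coded Aim 1 coefficient with the product term in the model.* This rests on two cells of 54 and has twice the marginal variance, so the ratios are 2, 4 and 8. Dividing z by √2, 2 and √8 gives .86, .57 and .33.

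**The case against.** **No stated figure is contradicted.** The plan names no interaction size, so it can be wrong only against a size that the reader supplies. This stands in part. A reader might infer that the claim is false for every interaction; the documents do not support that, because a large enough interaction would be detectable. But 1.61 is the only binary effect in the plan, and the absence of any size or calculation is itself the defect.

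**The main-effect comparator is open.** The power calculation looks marginal, but the Aim 1 model estimates a reference-level coefficient. This stands, and both versions are in Step 5. On the more favourable one, the averaged 2-way term would have .86, but only if the .99 is granted; the reference-level 2-way and the 3-way terms would still have .57 and .33. The plan says above .99, so .99 is a lower bound.

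**Hypothesis 2 is directional.** One-sided testing would be consistent with it, but gives only about .21, .14 and .11.

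**The model may not be binomial.** The participation decision is listed under multinomial regression, whereas the power section defines a binary success. The plan should settle this, but the change is unlikely to raise power.

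**Two further inferences go too far.** A reader might suppose that a non-significant interaction will be reported as no race difference. The plan never says so, and it intends to probe the nature of the interactions. A reader might also infer from a Wald-based simulation that the 3-way term can never reach 80% power. That follows from the Wald test and from counting empty or full cells as non-rejections. The documents name no Wald test, and a likelihood-ratio test does reach 80%, although only at very large ratios.

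**Conclusion.** The concern holds in a bounded form. The Aim 2 power statement has no basis in the documents, and it is wrong for an interaction as large as the planned main effect, under either reading of the 2-way coefficient and with one- or two-sided testing. Equal cells favour the plan, since imbalance by race, phase or arm lowers power. Covariate adjustment could move the figures somewhat but would not close the gap.

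This is a should-fix, not a must-fix. Aim 2 is the secondary objective, no test or conduct step is affected, and one power statement changes. The main-effect figure above .99 is a separate matter and is not counted here.

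**What to change.** Delete the Aim 2 power statement. In its place give power by simulation, or the detectable interaction sizes, for the exact coefficients to be tested. State:

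- whether the primary outcome model is binomial or multinomial;
- the coding of race and of both interventions;
- whether the 3-way term is in the model when the 2-way terms are tested;
- the test and its sidedness;
- the assumed cell split among the 216 and the assumed cell rates.

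Keep the planned Aim 2 tests and the sample size. Report the interaction contrasts and the race-specific intervention effects with 95% CIs, described as estimates of limited precision. Correct the main-effect figure at the same time, as its own item.

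The cost is one simulation and a change of wording. The downside is that Aim 2 then carries a less favourable stated power.

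### The primary outcome is defined and powered as binary, but the modelling text uses the participation decision as its multinomial example; the primary model and the coding of *undecided* need to be stated

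*Combined protocol and SAP*

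**What the plan says.** Most of the document points to a binary primary outcome.

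- Background and Specific Aims describes the primary outcome as a rate of decisions to enroll.
- Power and Sample Size Estimates says that a success "is defined as a patient deciding to enroll". It uses a "GEE power analysis for nested binomial outcomes", with success probabilities of .25 and .35 and an odds ratio of 1.61.
- The same section then turns to differences "in effects of the interventions on other binary or continuous outcomes", which implies that the primary outcome is itself binary.
- Hypothesis 1a says "we will fit separate MLMs to examine continuous and binary outcomes" and does not mention a categorical outcome.

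The general modelling paragraph, which stands just before the heading Models for Aim 1, reads differently. For binary outcomes it says "We will use binomial logistic models for binary outcomes (e.g., trial offer", so its example is a secondary outcome. It then gives "multinomial logistic regression for categorical outcomes (e.g., patients' self-reported participation decision", with the categories yes, no and undecided. Apart from the structural equation models of the exploratory Aim 3, this is the only place where a model is named for the participation decision, and the only place where *undecided* appears.

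Hypotheses 1a and 1b are each supported by one significant coefficient. Hypothesis 1c expects a significant positive coefficient for the product term. Models for Aim 1 specifies one multi-level model per outcome.

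**The concern.** An analyst who follows the modelling paragraph literally fits a three-category model to the variable that the power section treats as two-valued. The model then has no single coefficient to which the Hypothesis 1a rule ("Outcomes will be significantly improved in the patient intervention group, relative to the usual care group") can be applied. Someone has to choose the reference category and the contrast that counts, and the plan does not make that choice. It could be made after the data are seen.

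The choice can change the answer. The booklet works on attitudes and question-asking, so it may plausibly move men from a flat no to undecided. Yes-versus-no then moves in favour of the intervention, yes-versus-undecided moves against it, and the share deciding to enroll stays where it was. Only the yes versus not-yes contrast corresponds to the proportions used for power.

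**Working it through.** **Inputs.** From the power section: 216 patients, success .25 and .35. Assumed: 1:1 allocation (216 / 2 = 108 per arm), two-sided .05, no clustering and no covariates. The document gives no undecided share, so five starting splits with undecided between 5% and 45% are used.

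**Step 1. The plan's effect size is a binary one.** OR = (.35 × .75) / (.65 × .25) = .2625 / .1625 = 1.615, and b = ln 1.615 = 0.48. Both agree with the plan and both are yes versus not-yes.

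**Step 2. What each model estimates.** Write y, n and u for the three shares in an arm.

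- Binomial model: the difference between arms in ln[y / (n + u)].
- Multinomial model, reference no: the differences in ln(y / n) and ln(u / n).
- Multinomial model, reference undecided: the differences in ln(y / u) and ln(n / u).
- Multinomial model, reference yes: the differences in ln(n / y) and ln(u / y). A helpful intervention now tends to give negative signs, so even the positive sign expected in Hypothesis 1c depends on the reference category.

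None of the multinomial coefficients is the binomial one.

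**Step 3. Worked example with yes unchanged.** Control 25/50/25 (yes/no/undecided, %), intervention 25/35/40, so 15 points move from no to undecided.

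- Yes versus no: ln(.50 / .35) = 0.357. Cell counts are 27, 54, 27 and 37.8, so SE = √(1/27 + 1/54 + 1/27 + 1/37.8) = 0.345 and the expected z is 1.03. P(z > 1.96) = Φ(1.03 − 1.96) ≈ .18.
- Yes versus undecided: ln(.25 / .40) = −0.470. SE = √(1/27 + 1/27 + 1/27 + 1/43.2) = 0.366 and the expected z is −1.28. It is significant against the intervention in about .25 of trials.
- Yes versus not-yes: ln 1 = 0, so it is significantly favourable in about .025.

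**Step 4. All splits.** Share of trials in which yes versus no significantly favours the intervention while yes stays at .25 in both arms (200,000 simulated trials per cell, Wald tests, z > 1.96):

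| Control yes/no/undecided (%) | 5 points | 10 points | 15 points |
|---|---|---|---|
| 25/70/5 | .041 | .069 | .112 |
| 25/60/15 | .044 | .078 | .138 |
| 25/50/25 | .050 | .096 | .176 |
| 25/45/30 | .052 | .108 | .208 |
| 25/30/45 | .070 | .177 | .397 |

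The binary test gives .024-.025 throughout. In the 15-point column, yes versus undecided is significant against the intervention in 14% to 75% of trials.

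**Step 5. When yes truly rises from .25 to .35.** Power of yes versus no is .16-.19 if the added men come from undecided, .26-.35 if they come proportionally from both groups, and .36-.51 if they come from no. The binary test has about .36 in each case. The multinomial contrast may do worse or better.

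**The case against.** The strongest reply is that the plan already answers the question. The primary outcome is a rate, a success is a man who decides to enroll, power is binomial, the other outcomes are called binary or continuous, and Hypothesis 1a is limited to those two types. On ordinary reading an undecided man has not decided to enroll. The multinomial sentence is only an example, stands in a general paragraph before Models for Aim 1, and does not call the self-reported item the primary variable. The post-visit questionnaire and the follow-up interview are appendices that are not shown, and the Time 4 record review lists completing enrollment procedures separately from enrolling, so another measure of the decision may exist.

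Most of this stands. A reader might infer that the plan commits the primary test to a multinomial model; the document does not support that, and a binary test is the likelier intention. What remains is that no sentence assigns the binomial model to the primary outcome, and that the only model named for the decision outside Aim 3 does not fit the single-coefficient rules. If another variable is primary, the plan should name it.

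A reader might also infer an inflated type I error or a loss of power. Neither is supported. Nothing says that yes versus no is the readout, or that either yes-coefficient may count. If either did count, the favourable null rate would be 3.7-4.4% instead of 2.5%, but that rule is not in the plan. The rates in Step 4 are not false positives for the yes-versus-no odds, which do change in those scenarios. They show that a different quantity is being tested. Step 5 shows no consistent power loss.

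**Conclusion.** The point holds as a mismatch between the outcome as defined and powered and the one model named for it in the general modelling text, together with an unstated coding of *undecided*. It does not show that the primary analysis would be run as multinomial.

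The consequence is conditional on the multinomial model being used and yes versus no being read as support. A favourable result with no change in the share deciding to enroll would then occur in 4-7%, 7-18% or 11-40% of trials for moves of 5, 10 or 15 points, against about 2.5% for the binary test. These figures rest on 108 per arm, no clustering, and assumed splits and shifts; at 5 points the effect is small. The plan should be corrected because the change is cheap and removes a choice that could otherwise be made after seeing the data.

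Two neighbouring questions are separate and are not settled here: the stated power above .99, and whether the primary analysis takes patients with whom a trial was discussed or all those eligible and randomized.

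**What to change.** In the general modelling paragraph and under Hypotheses 1a to 1c, state that:

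- the primary analysis is a multi-level binomial logistic model of decided to enroll, with yes = 1 and no or undecided = 0;
- Hypotheses 1a to 1c for the primary outcome are judged from this model;
- the three-category multinomial model is supportive, with its reference category named.

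The coding of the intervention terms must be settled at the same time. In logit P(yes) = b0 + b1·patient + b2·physician + b3·patient × physician with 0/1 dummies, b1 is the patient-intervention effect before the physician intervention only; afterwards it is b1 + b3. Likewise b2 is the physician-intervention effect in usual care only. Neither is a main effect while the product term is in the model. Either use centred coding (−½, +½), which makes the patient coefficient the average b1 + b3/2 (and the physician coefficient b2 + b3/2) and leaves b3 unchanged, or state that Hypotheses 1a and 1b concern the simple effect in the reference phase or group.

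A prespecified contrast in P(yes) from the multinomial model would also serve. The binomial model is suggested because it matches the outcome as powered.

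Cost: a few sentences and no new data. The downside is that the primary result does not separate no from undecided, which the supportive model still reports.
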